2.8 Specific Drug Supply Requirements

Imipenem-Cilastatin-Relebactam 1.25 gram vials (n=15 vials)

2.9 Adverse Experience Reporting
	
Participants will be monitored for any sign or symptom of adverse events throughout the course of the study. Unanticipated, life-threatening or fatal adverse events will be reported to the IRB, the manufacturer, and the Food and Drug Administration according to federal guidelines. All adverse events requiring medical attention will be treated by the study physician and will be recorded by the investigator.
 
For the purpose of this study, an adverse event will be defined as any pathologic or unintended change in the structure (signs), function (symptoms), or chemistry (laboratory values) of the body associated with the use of the study drug, whether or not considered drug related, and will be categorized as one of the following:
 
 • MILD – present, but easily tolerated • MODERATE – discomfort that interferes with usual activities • SEVERE – incapacitating, inability to work or do usual activities 
Relationship of the AE to the study medication (i.e., causality) will be evaluated according to the investigator’s opinion, as one of the following:
 
 • Concurrent condition – unrelated to study drug • REMOTE adverse drug event – little or no temporal relationship to study drug • POSSIBLE adverse drug event – temporal relationship to study drug • PROBABLE adverse drug event – commonly associated with study drug • DEFINITE adverse drug event – reappeared on re-challenge of study drug 
All SAEs will be reported to the Institutional Review Board, sponsor, and the Food and Drug Administration according to Federal and local guidelines. A serious adverse event will be defined as any adverse event that results in death, is immediately life-threatening, requires or prolongs hospitalization, or is an important medical event that may jeopardize the participant or may require medical intervention to prevent one of the previously mentioned outcomes.

2.10 Itemized Study Budget
	
See Proposed Budget

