2.1 Objectives

1. Determine the single-dose pharmacokinetics of intravenous imipenem (when administered as imipenem-cilastatin-relebactam 1.25 grams as a 30 minute infusion) in adult critically ill patients with known or suspected sepsis and ARC
2. Determine the single-dose pharmacokinetics of intravenous relebactam (when administered as imipenem-cilastatin-relebactam 1.25 grams as a 30 minute infusion) in adult critically ill patients with known or suspected sepsis and ARC
3. Determine a dose of imipenem-cilastatin-relebactam that achieves greater than 90% probability of pharmacodynamic target attainment using the imipenem *P. aeruginosa* susceptibility breakpoint of 2 µg/mL and the MIC distribution of a contemporary *P. aeruginosa* and KPC producing *K. pneumoniae* population
4. Assess the safety and tolerability of single-dose imipenem-cilastatin-relebactam in adult critically ill patients with known or suspected sepsis and ARC

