
2.5 Study Procedures
	
Study Locations The Center for Anti-Infective Research and Development (CAIRD), Hartford Hospital, CT will coordinate the study. The study will be conducted in the medical, surgical, and neurosurgical ICUs at Hartford Hospital, an 890 bed tertiary care hospital in Hartford, CT. Institutional Review Board approval will be required based on local regulations. If LAR or next of kin are consented, local regulations will be followed to collect written informed consent from the patient once able to provide consent.
 
Study Population Inclusion Criteria Patients eligible to participate in the study must meet all of the following criteria prior to any study-related procedure:
 
 1. Male or female aged 18-54 years; 2. APACHE II score ≥ 10 and ≤ 35; 3. Creatinine clearance (CrCL) ≥ 130 mL/min (as calculated by the Cockcroft-Gault equation using ideal or adjusted body weight) within 24 hours of dosing (Note: using a higher CrCL threshold for Cockcroft-Gault CrCL will increase likelihood that enrolled participants have a urine CrCL ≥ 130 ml/min/1.73 m² and thus qualify as ARC); 4. Documented infection or presumed infection by receiving another antibiotic. 
Exclusion Criteria Patients will be considered ineligible if they meet any of the following criteria:
 
 1. If female, currently pregnant or breast feeding; 2. History of any moderate or severe hypersensitivity or allergic reaction to any β-lactam antibiotic (Note: mild rash or erythema to penicillin or cephalosporin antibiotics would not disqualify a patient if they have received a carbapenem without problem); 3. History of chronic kidney disease, hemodialysis, or peritoneal dialysis; or history of acute renal replacement therapy (e.g., hemodialysis,

hemofiltration, hemodiafiltration) or extracorporeal membrane oxygenation (ECMO) associated with current illness;

4. Suspected rhabdomyolysis or creatine kinase > 10,000 U/L;
5. Any serum creatinine (SCr) before dosing that is increased ≥ 0.3 mg/dL from the baseline SCr used qualifying for enrollment;
6. Urinary output <20 ml/hour for at least 2 hours (oliguria) within 24 hours before enrollment;
7. Sustained (at least 1 hour) hypotension (systolic pressure < 90 mmHG or mean arterial pressure < 55 mmHg) refractory to vasopressors or IV fluid resuscitation for at least 24 hours before enrollment;

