All participants will receive a single dose of imipenem-cilastatin-relebactam 1.25 grams as a 30 minute (+/- 5 minutes) infusion. Imipenem-cilastatin-relebactam vials will be supplied by the study sponsor. The dose will be prepared according to manufacturer recommendations in precisely 100 ml of 0.9% sodium chloride. Imipenem-cilastatin-relebactam must be administered through a peripheral intravenous catheter, peripherally inserted central catheter (PICC), central line, or port-a-catheter, whichever is determined to be most appropriate by the local investigator and care provider for each participant. Participants will also receive standard intravenous antibiotic therapy (excluding generic or branded intravenous imipenem) to treat their suspected infection, as determined by the responsible provider. No other intravenous medications will be co-administered with imipenem-cilastatin-relebactam.

Study Day 1

- Within 8 hours of beginning study medication infusion, a pre-dose SCr will be collected to confirm calculated CrCL remains ≥130 mL/min and that no change in SCr was observed to be ≥ 0.3 mg/dL from the baseline SCr used qualifying for enrollment.
- An 8 hour (± 1 hour) urine creatinine collection will be initiated within 4 hours prior to study medication infusion. The results of the measured urine CrCL will be used to confirm ARC in the patient over the time period that blood samples for imipenem-cilastatin-relebactam are collected.

$$\text{Measured CrCL (ml/min)} = \frac{\text{UCr (mg/dL)} \times \text{urine volume (mL)}}{\text{Predose-SCr} \times \text{time}^a}$$

Abbreviations: CrCl = creatinine clearance; SCr = serum creatinine; UCr = urine creatinine.

^a Time = The 8-hour urine collection has a ± 1 hour window (i.e., 480 min \pm 60 min); use the exact number of minutes of the urine collection in the equation

- Vital signs (temperature, heart rate, blood pressure, respiratory rate) will be recorded within 15 minutes prior to starting the study drug infusion.
- Participants will receive the single dose of imipenem-relebactam as described above. Exact start and stop times will be recorded in military time.
- Identify, assess, and record any new adverse events or Serious Adverse Events (SAE)
- Concomitant medications will be recorded.

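### Section 2.9's severity and causality scales fit a single-dose ICU study poorly, so the grades reported for objective 4 risk being inconsistent or uninformative

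*Combined protocol and SAP*

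**What the plan says.** Objective 4 in Section 2.1 is to "Assess the safety and tolerability of single-dose imipenem-cilastatin-relebactam in adult critically ill patients with known or suspected sepsis and ARC".

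Section 2.9 supplies the only grading rules for that objective.

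- **What counts as an adverse event.** The definition covers signs, symptoms and "chemistry (laboratory values) of the body associated with the use of the study drug".
- **Severity, three grades.** MILD is judged by how easily the event is tolerated. MODERATE is discomfort that gets in the way of what the patient normally does. The top grade reads "SEVERE – incapacitating, inability to work or do usual activities".
- **Causality, five categories, assigned on the investigator's opinion.** These are a concurrent condition unrelated to the drug; REMOTE (little or no link in time); POSSIBLE (a link in time); PROBABLE (an event the drug commonly produces); and "DEFINITE adverse drug event – reappeared on re-challenge of study drug".

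The design these scales must serve is in Section 2.5: "All participants will receive a single dose of imipenem-cilastatin-relebactam 1.25 grams as a 30 minute (+/- 5 minutes) infusion". Background antibiotics are allowed, "excluding generic or branded intravenous imipenem". Patients are in medical, surgical and neurosurgical ICUs, with "APACHE II score ≥ 10 and ≤ 35". Chemistry, liver, blood count and urine panels are taken at screening and repeated on Study Day 2.

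**The concern.** A causality scale should order events by how strong the evidence is, and a severity scale should order them by how bad they are. Neither scale does this reliably here. The top causality category asks for something the design never supplies. The category below it asks how often the reaction is seen in general, not how well this case is evidenced. Two severity grades refer to activity and work in patients who are in intensive care before they are dosed.

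What is at stake is the interpretability of objective 4. There is no concurrent control arm, the safety population is at most about 12, and Section 2.7 defines that population without specifying any safety summary. Rates cannot be set against a comparator, so the reader of the results will lean on case-by-case severity and causality. Section 2.2 also says that, to the authors' knowledge, relebactam pharmacokinetics have not been studied in critically ill patients with ARC, so a reaction not already known to be common deserves a fair grade.

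**Working it through.** The plan's one statistical calculation, the power in Section 2.7, concerns clearance and does not enter this point. The check is to set each category of Section 2.9 beside the design in Section 2.5.

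**Causality**

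| Category | Condition, paraphrased | Available after one dose? |
|---|---|---|
| Concurrent condition | Unrelated to drug | Yes |
| REMOTE | Little or no link in time | Yes |
| POSSIBLE | Link in time | Yes; nearly any event after the dose on Days 1–2 satisfies it |
| PROBABLE | Reaction commonly seen with drug | Yes, but only for common reactions |
| DEFINITE | Recurs on re-challenge | No |

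The only route to DEFINITE would be a further exposure. No repeat dose is described, and other intravenous imipenem is excluded from background therapy. Section 2.8 orders 15 vials for up to 12 patients, leaving 15 − 12 = 3 spare, but no procedure uses them for a second dose. So 1 of 5 categories is unreachable and 4 of 5 remain.

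Now take an uncommon reaction that starts during the infusion, has a plausible mechanism and resolves afterwards. It cannot be DEFINITE (no re-challenge) or PROBABLE (not common), so it is POSSIBLE. An event of uncertain origin a few hours later also meets POSSIBLE on timing alone. Two cases with very different evidence carry the same label. The categories also rest on different things (timing, general frequency, re-challenge) and overlap: a common reaction with the right timing meets both POSSIBLE and PROBABLE.

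**Severity**

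| Grade | Anchor, paraphrased | Use in this population |
|---|---|---|
| MILD | Easily tolerated | Usable, with difficulty if the patient cannot report |
| MODERATE | Discomfort limiting normal activities | Hard to separate from existing illness |
| SEVERE | Incapacity; unable to work or carry on as normal | Hard to separate from existing illness |

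So 2 of 3 grades lean on activity or work.

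**Laboratory changes**

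None of the three anchors refers to a laboratory value. Read literally, a symptom-free transaminase rise is easily tolerated and so MILD, whether it is just above normal or beyond 5 times the upper limit, the level that exclusion 11 itself uses to define acute liver injury. The plan sets laboratory thresholds for eligibility but none for grading what happens after the dose.

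**What does not depend on the scales**

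Counts of events can be reported without either scale. With 12 patients and no event of a given type, the exact one-sided 95% upper bound is 1 − 0.05^(1/12) = 22.1%. With a true rate of 10%, the chance of seeing at least one event is 1 − 0.9^12 = 71.8%. Neither figure uses a grade. Serious adverse events have their own outcome-based definition in Section 2.9.

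**The case against.** The case for leaving Section 2.9 alone has real force on several points, and a reader could infer more than the documents support.

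- **That unrelated ICU events must default to POSSIBLE.** They need not. The first category is for concurrent conditions, carries no timing requirement, and is open to the investigator's judgement.
- **That no enrolled patient can perform any usual activity, or that every patient is sedated.** The plan does not describe baseline function. APACHE II may be as low as 10, some patients are expected to consent for themselves, and ventilator support is recorded, not required. The anchors are weak for this population; how many patients they fail is unknown.
- **That the scales are unusable and events will be misgraded.** An empty top category does not by itself assign a wrong grade, and four categories remain. A grade describes the event, so a patient already incapacitated by sepsis does not make a laboratory rise incapacitating, and MILD can take a symptom-free change. Inconsistency is a risk, not a certainty.
- **That objective 4 is lost.** Serious adverse events are classified and reported by outcome, laboratory panels bracket the dose so change can be described directly, and 12 patients can be listed individually. No stopping rule, endpoint or test uses a grade.

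All of this limits the size of the point. It does not answer the core: DEFINITE is empty, PROBABLE excludes uncommon reactions, and laboratory changes have no graded criterion. Investigator opinion does not repair this, because constraining opinion is what a defined scale is for.

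**Conclusion.** The concern holds in a limited form. One of 5 causality categories cannot be reached by any of the up to 12 participants, a well-evidenced but uncommon reaction is held at POSSIBLE, 2 of 3 severity grades rest on activity or work anchors, and no grade is written for laboratory changes. The consequence is a risk of inconsistent or uninformative severity and causality grades for objective 4. Event counts, and the classification and reporting of serious adverse events, stand.

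This rests on reading the category definitions as necessary conditions, on the absence of any second dose in the plan, and on the inference from the ICU setting and APACHE II range that activity and work discriminate poorly. It should be changed, because the defect lies in stated rules and the remedy is cheap, but it does not touch the pharmacokinetic objectives.

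**What to change.** Amend Section 2.9 and the case report form.

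1. Replace the severity scale with a standard graded toxicity scale that covers laboratory values, and state that the grade reflects change from the patient's own baseline.
2. Redefine PROBABLE and DEFINITE by evidence obtainable after one dose: timing relative to the infusion, subsequent course, a plausible mechanism or known reaction, and whether another cause is more likely. Remove re-challenge and general frequency as necessary conditions.

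No extra visits, samples or staff are needed, and dosing is untouched. The cost is a slightly longer scale for graders to learn. Few events may reach the top causality category in patients with infection, other antibiotics and many competing causes, but that would then reflect the evidence and not the wording.

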2.13 Protocol Submission for Investigator-Initiated Studies	
U.S. protocols should be submitted by US investigators directly or through the Global Research Specialist at www.merckiiisp.com
 
Non U.S. protocols should be submitted to the MSD office by the investigators.

